4.1 General Statistical Methods

The statistical analyses will be presented by treatment group for the different analysis sets as defined in [section 3](#).

Summary tables will be structured with a column for each treatment in the order (asapiprant, Placebo, Total).

Continuous variables will be summarised using descriptive statistics, i.e., displaying number of patients in the respective analysis population, number of patients with data, mean, median, standard deviation (SD), minimum, and maximum.

Categorical variables will be summarised by using frequency counts and percentages. In addition, the number of patients with missing values will be displayed. Unless specified, the denominator for percentages will be the number of patients in the analysis set and treatment group under consideration.

Means and medians will be reported at 1 more significant digit than the precision of the data. Standard deviations and confidence intervals (CIs) will be reported at 2 more significant digits than the precision of the data. Minimum and maximum will be reported to the same level of precision as the original observations. Percentages will be presented to 1 decimal place if not otherwise stated.

QMS Document Name: Statistical Analysis Plan	Page 12 of 27
QMS No (include version ref): STF-015-GL.02	Document date: 09JUL2019
CONFIDENTIAL	

If the number of patients in a category is 0, then percentage will not be displayed, and only a count of 0 will be shown.

All p-values will be two-sided and reported to 4 decimal places at least. Values less than 0.0001 will be displayed as <0.0001.

In listings, data will be sorted by treatment, site, and patient ID, and when appropriate by visit or other identifiers for sequence or type of observation.

The confidence level for calculation of CIs will be chosen as (1-significance level) of the respective statistical test.

If a qualitative parameter in a table has missing values, a row with the number of missing values will be added.

Factor 365.2425 is used for duration conversions between days and years. Factor 30.436875 is used for duration conversions between days and months.

4.2 Covariates and Strata

The primary endpoint (proportion who have died or progressed to RF at 28) will be analyzed using a logistic regression with treatment group and covariates, age group (50 to < 75 years, and \geq 75 years), and region. Other covariates including previous COVID-19 therapy may be explored as exploratory analyses.

4.3 Subgroups

The following sub-groups will be examined for the primary endpoint. Results will be displayed in both tabular form. Subgroup analyses are exploratory.

- Age (50 to < 75 vs \geq 75)
- Gender (male vs female)
- previous COVID-19 therapy (yes vs no)
- Regions (North America vs South America)
- Baseline WHO ordinal clinical scale (3 or 4)

4.4 Missing Data

In general, missing data will not be imputed except partial and missing dates as specified below. The data will be analyzed as they are recorded.

Details of handling missing primary endpoint are addressed in section [10.1](#) primary analysis.

WHO Ordinal Scale for COVID-19 scores will be analyzed by carrying forward any early deaths to Day 28.

Partial or missing dates and times

The missing component(s) of incomplete dates (e.g., start and/or stop dates of AE, concomitant medication, medical history) will be assumed as the most conservative value possible. For example, if the start date has a missing day value, the first day of the month will be imputed for study day computations, etc. If day is missing for an end date, the last day of the month will be imputed. If the start date has a missing month value, the first month of the year will be imputed for study day

QMS Document Name: Statistical Analysis Plan	Page 13 of 27
QMS No (include version ref): STF-015-GL.02	Document date: 09JUL2019
CONFIDENTIAL	

computations, etc. If month is missing for an end date, the last month of the year will be imputed. For determination of treatment-emergent status, the start date will be imputed as the date of the first dose of study drug, unless there is clear evidence (through comparison of partial dates/times) to suggest otherwise.

Date imputation will only be used for computational purposes such as treatment-emergent status, etc. Actual date values, as they appear in the original electronic case report forms (eCRFs), will be presented in the patient data listings.

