### **7.1.2.2 End of Treatment, Follow-up and End of Study Period**

The end of treatment visit is the date when the subject has completed the final study treatment as outlined in the schedule of assessments.

There is a follow-up visit to occur at Day 28 (approximately 14 days after the final dose of study drug).

The end of study visit is to occur on Day 57 (approximately 43 days after the final dose of study drug). This visit will be a telephone call initiated by the site staff to query for SAEs, AEs, and concomitant treatments. All AEs and SAEs that are not resolved through 30 days after the last dose of study drug will be followed to closure (see [Appendix 3.2](#)).

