### **8.4 Statistical Analysis Process**

The study will be analyzed by the Sponsor (or a nominated designee).

The primary endpoint (proportion who have died or progressed to RF at Day 28) will be analyzed using a logistic regression with treatment group and covariates, age group (50 to <75 years, and > 75 years), baseline WHO ordinal clinical scale (3 or 4), and region. Other covariates including previous COVID-19 therapy may be explored. Estimation of the covariate-

adjusted difference in proportion responding will be reported using Cochran-Mantel-Haenszel (CMH) weighting and estimates from the logistic regression (LR) as described by Ge and colleagues (Ge et al., 2011, Appendix C). This analysis will be repeated without the covariate. Deaths prior to Day 28 will be included in the endpoint (RF, death). WHO Ordinal Scale for COVID-19 scores ([Table 2](#)) will be analyzed by carrying forward any early deaths through Day 28; other categorical and continuous outcomes will be described. The primary analysis will be based on the Intent-to-Treat population (ITT), analyzed as randomized. The denominator for the proportions alive and RF-free at Day 28 will include all randomized subjects. Subjects lacking sufficient data to confirm RF-free and alive at Day 28 will be included in the primary analysis as treatment failures. If more than 5% of subjects have insufficient data to confirm RF-free and alive at Day 28, BioAge will employ a MI strategy (SAS MI, MIANALYZE) based on the patients last known status. For example, the last known WHO Score for a patient lost to follow-up can be used to impute missing primary outcome from patients with known primary outcome and similar WHO Scores. For the primary comparison, analysis by treatment group will be, “as randomized”. Secondary analyses of the primary endpoint may be repeated for the mITT and the per protocol populations, analyzed as treated. Time-to-RF will be analyzed using methods of Kaplan-Meier (KM), with time zero at randomization. Hazard ratios (Cox PHREG) with 95% confidence intervals will describe the treatment effect.

A sensitivity analysis may be completed to assess concurrent treatments and prior SARS-CoV-2 vaccinations in relation to the primary endpoint.

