4.5 Visit Windows

The following table outlines the analysis visits that data will be mapped to for analysis of efficacy, safety and pharmacodynamics data collected during the study. If after mapping, multiple data points share the same analysis visit, the data point closest to the expected study visit will be used. If there is a tie, the earlier of the visits will be used.

Study Visit	Analysis Visit	Analysis Window
Screening	Screening	-3 to -1
Days 1 – 13	Days 1 – 13	0
Days 14	Days 14	+2 day
Day 28 Follow-up	Day 28	± 2 day
Day 57 Phone Follow-up Visit	Day 57	± 4 day

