4.7 Definition of Baseline Values

The baseline value is defined to be the last non-missing assessment prior to randomization. For baseline WHO ordinal scale, if not collected prior to randomization, the earliest collected WHO ordinal scale collected on the same day as randomization will be used as baseline. Pre-randomization assessments on the same day as randomization will be considered the baseline assessment for each of these respective study procedures. Unless otherwise specified, change from baseline calculations for a treatment window assessment will be the applicable treatment window assessment minus the

baseline assessment. If either the treatment window assessment value or the baseline value is/are missing, then change from baseline will be set to missing.

Age in years will be calculated as (date of informed consent – January 01 of year of birth) / 365.2425.

4.8 *Planned Analyses*

The following statistical analyses are planned for this study:

- Unblinded safety analyses for Data Monitoring Committee (DMC): An independent DMC will be utilized throughout the study to monitor patient safety. DMC meetings for safety will be conducted after 33, 100, and approximately 208 subjects complete assessments through the 28-day follow up (Day 28), approximately 14 days after the final dose of study drug. A DMC charter will be developed preceding study initiation and will define DMC processes and meetings, and required report contents.
- Interim analysis: An interim look for safety and primary endpoint will be conducted by the DMC when approximately 208 patients in the ITT population complete assessments through the 28-day follow up (Day 28), approximately 14 days after the final dose of study drug.

When all subjects enrolled under the targeted or adjusted sample size have completed the study through Day 28 (i.e., full study enrolment is completed), the clinical database will be cleaned, frozen, and an assessment of the primary efficacy endpoint and secondary, exploratory, and safety endpoints up to Day 28 in the ITT population will be created. Individuals involved with the conduct of the study will not have access to unblinded data until database lock. Final analysis: final analysis on efficacy and safety will occur after the database is locked.

4.9 *Multiple Comparison/Multiplicity*

No multiplicity adjustment is planned.

5 Study Population and Disposition

5.1 *Analysis Population*

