10.2 Secondary efficacy analyses

All secondary efficacy endpoints will be analyzed without adjustment for multiplicity using ITT and mITT and PPS (if formed) under randomized treatment based on the data observed. No missing data will be imputed unless specified otherwise.

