10.2.1 Proportion of binary endpoints

The number and percentage of the following binary endpoints will be presented by treatment and timepoint. Comparison of proportion of patients between treatment at each timepoint will be analysed by the same manner as primary endpoint.

- Proportion of patients who had survived at each timepoint at Day 14, at Day 28, at Day 57: which is defined as patients who had no documented death prior or on timepoint at Day 14, 28, 57.
- Proportion of patients who survive without progression to RF at each timepoint at Day 14, Day 28, Day 57: which is defined as patients who had neither documented death nor respiratory failure prior or on timepoint at Day 14, 28, 57.
- Proportion of patients who had intubation during the study: which will be defined as proportion of patients who had any documented intubation during the study.
- Proportion of patients who develop critical COVID-19 illness as defined by at least one the following:
 - A. Respiratory failure defined based on resource utilization requiring at least one of the following: Endotracheal intubation and mechanical ventilation, oxygen delivered by high-flow nasal cannula (heated, humidified, oxygen delivered via reinforced nasal cannula at flow rates > 20 L/min with fraction of delivered oxygen ≥ 0.5), noninvasive positive pressure ventilation, ECMO clinical diagnosis respiratory failure (i.e., clinical need for one of the preceding therapies, but preceding therapies not able to be administered in setting of resource limitation)
 - B. Hemodynamic compromise (defined by systolic blood pressure < 90 mm Hg, or diastolic blood pressure < 60 mm Hg or requiring vasopressors)
 - C. Multi-organ dysfunction/failure
- Proportion of patients requiring intensive care unit admission: which is defined as patients who had been admitted to intensive care unit during the study.
- Incidence of supplemental O₂ administration: which will be defined as proportion of patients who had any documented post-dosing supplemental O₂ administration during the study.
- Incidence of noninvasive ventilation or high-flow nasal cannula O₂ administration: which will be defined as proportion of patients who had any documented post-dosing noninvasive ventilation or high-flow nasal cannula O₂ administration.
- Incidence of mechanical ventilation: which will be defined as proportion of patients who had any documented post-dosing mechanical ventilation.

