Mean change in WHO Ordinal Scale at Day 14, 28, and 57 will be analyzed using ANCOVA on change at each time point. The model will include the stratification factors. The least squares means (LS-means) for each treatment, LS-means treatment difference and corresponding CI for the LS-means difference and p-value for the treatment difference, will be reported at the Day 14, 28, and 57.

Results from Wilcoxon rank sum test and t-tests will also be reported for change in WHO Ordinal Scale at the Day 14, 28, and 57.

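### Deaths have no assigned WHO score at Day 57, and the SAP measures support duration by the first episode only, where the protocol counts days per subject

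*SAP*

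**What the plan says.** **WHO score at Day 57.** The SAP's only rule for deaths on this scale is "WHO Ordinal Scale for COVID-19 scores will be analyzed by carrying forward any early deaths to Day 28" (SAP 4.4). Protocol 8.4 agrees: scores "will be analyzed by carrying forward any early deaths through Day 28; other categorical and continuous outcomes will be described". SAP 10.2.3 goes further in time: "Mean change in WHO Ordinal Scale at Day 14, 28, and 57 will be analyzed using ANCOVA on change at each time point", with Wilcoxon and t-tests added. For secondary endpoints, "No missing data will be imputed unless specified otherwise" (SAP 10.2). SAP 4.7 adds: "If either the treatment window assessment value or the baseline value is/are missing, then change from baseline will be set to missing". SAP 4.5 lists the "Day 57 Phone Follow-up Visit" with a window of ±4 days, and protocol 7.1.2.2 explains: "This visit will be a telephone call initiated by the site staff to query for SAEs, AEs, and concomitant treatments". Protocol Table 1 does schedule the WHO scale at Day 57, and death is score 8 on that scale.

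**Durations.** For the endpoints titled incidence and duration, protocol 8.4 tallies days for each subject and compares arms by Wilcoxon and t-tests. SAP 10.2.4 defines the duration of intubation, supplemental oxygen, noninvasive ventilation or high-flow oxygen, mechanical ventilation, and ventilation plus organ support from the start and end dates of the first episode after dosing. It names the ITT and PP sets but describes the analyses as exploratory and as subset analyses. It has no zero-day rule, no summing of later episodes and no rule for death during an episode. SAP 1 says the SAP prevails where the two documents differ. Incidence, in SAP 10.2.1, is any documented episode among all patients.

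**The concern.** At Day 57, a subject who died on Day 10 counts as 8 at Day 28 and then disappears. A subject alive at Day 28 who dies on Days 31-52 has no value in the Day 57 window, so that death enters none of the three WHO mean-change comparisons. Removing the worst outcome can hide a survival difference in either direction. It can also make both arms appear to improve after Day 28 when no survivor has changed.

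For durations, comparing only subjects who had an episode compares groups formed after randomisation. A drug that prevents the shorter episodes leaves the longer ones in its arm and can look worse for having worked. This is most serious for intubation and ventilation. It matters less for supplemental oxygen, which the entry criteria permit and many subjects may already receive.

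**Working it through.** **Plan's own figure.** Neither document states a figure for these endpoints. The nearest is N = 312 for the primary endpoint (31% vs 15%, two-sided 5%, 90% power, Fisher's exact test). It reproduces: the continuity-corrected formula gives 156 per arm, and exact Fisher power there is 0.905. Nothing below changes it.

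**Which Day 57 values exist.** The window is 57 ± 4, that is Days 53-61. The Day 28 window is 28 ± 2, that is Days 26-30. Following SAP 4.4, 4.5, 4.7 and 10.2 together:

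| Death | Day 28 value | Day 57 value |
|---|---|---|
| By Day 28 | 8, carried | none assigned; change missing |
| Days 31-52 | score while alive | none assigned; change missing |
| Days 53-61 | score while alive | 8 only if recorded in the window |

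**Size at Day 57.** Assumed: baseline 4; survivors improve by 2.5 in both arms with SD 1; a death is a change of 8 - 4 = +4; illustrative 104 per arm (half of 208). With mortality d:

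- Mean change per arm = (1-d)(-2.5) + d(4), so the difference (active minus placebo) = -6.5 × (d_placebo - d_active).
- Variance per arm = (1-d)(1) + d(1-d)(6.5²).

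| Mortality, placebo vs active | Difference, deaths = 8 | SE | Difference / SE | Survivors only |
|---|---|---|---|---|
| 5% vs 2.5% | -0.16 | 0.22 | 0.7 | 0 |
| 10% vs 5% | -0.33 | 0.27 | 1.2 | 0 |
| 15% vs 7.5% | -0.49 | 0.31 | 1.6 | 0 |

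For the middle row, the variances are 4.70 and 2.96, and SE = √((4.70 + 2.96)/104) = 0.27. At 60 per arm the SE is 0.36 (ratio 0.9).

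*Apparent improvement.* If those 10% and 5% die by Day 28 and no survivor changes afterwards, the mean changes at Day 28 are -1.85 and -2.175. Dropping the deaths moves both to -2.5 at Day 57, shifts of -0.65 (placebo) and -0.33 (active) with no change in anyone alive.

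**Size for durations.** Assumed: 16 placebo and 8 active subjects of 104 ventilated, one episode each; the 8 prevented cases would have lasted 10 days and the other 8 last 20.

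- Among the ventilated: placebo (8×10 + 8×20)/16 = 15; active 20; difference +5.0 days.
- All randomised, total days: 240/104 = 2.31 vs 160/104 = 1.54; difference -0.77 (SE 0.77; Wilcoxon p = 0.11).
- Range: prevented cases of 5 days and others of 20 give +7.5 and -0.38; all cases of 15 days give 0 and -1.15.

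*Later episodes.* If 10-30% of those with an episode have a second one of 7 days, the first-episode rule understates their mean by 0.1×7 = 0.7 to 0.3×7 = 2.1 days.

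**Dependence on sample size.** The all-15-day case gives Wilcoxon p = 0.08 at 104 per arm (16 vs 8 ventilated) and p = 0.034 at 156 per arm (24 vs 12).

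**The case against.** The strongest reply on Day 57 is that death is a category of the scale and the scale is scheduled at that visit. A site could record 8, and it would be analysed as recorded. That is fair: neither document excludes deaths, and a reader who infers a stated exclusion goes too far. But the plan needed an explicit rule to place deaths at Day 28 and ended it there, and no rule supplies an 8 to someone who died weeks before the call. Nor is this half a conflict between the documents, since both stop at Day 28.

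On durations, a reader might infer that the SAP restricts the analysis to subjects with an episode. It does not say so, and it names the ITT set. The omission follows from durations built on episode dates with no zero-day rule and no imputation. The protocol does not state zeros either, so only the first-episode limit is a clear narrowing of it. A reader might also extend the first-episode rule to incidence, which SAP 10.2.1 does not support.

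It is also tempting to treat 104 per arm as a ceiling because enrolment stopped before the interim (SAP 16). The interim is triggered by about 208 patients completing Day 28, so more could have been randomised by then.

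Finally, protocol 8.4 names no key secondary endpoint and corrects none for multiplicity. Day 57 survival is reported separately, so a mortality difference is not hidden from the trial as a whole. All of that stands and limits the weight of the point.

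**Conclusion.** The point holds as a gap at Day 57 and as an unexplained narrowing of the protocol for durations. Followed as written, the plan gives an essentially survivors-only WHO comparison at Day 57. It also gives support durations that omit later episodes and, by default, subjects who had none.

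Under the assumed inputs, the Day 57 analysis loses a difference of 0.16 to 0.49 points, and duration among the ventilated differs by 0 to +7.5 days when total days favour the drug by 0.38 to 1.15. Mortality, survivor change, episode length and numbers ventilated are all assumptions. Whether such differences would reach significance depends on the number actually randomised, which the documents do not give. The primary analysis and N = 312 are untouched. This should be corrected, but it does not threaten the trial's main conclusion.

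**What to change.** Make both changes in a dated SAP amendment before unblinding.

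(a) In SAP 4.4, assign score 8 from the date of death through Day 57, including deaths after Day 28. This needs no new data: the Day 57 survival endpoint in SAP 10.2.1, "which is defined as patients who had no documented death prior or on timepoint at Day 14, 28, 57", already requires these deaths.

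(b) In SAP 10.2.4, for the five support-duration endpoints, define duration as total days over all post-dosing episodes per randomised subject, 0 if none, with death closing an episode. Make the already planned Wilcoxon test the main comparison and keep ANCOVA and the t-test as supportive. Show durations among subjects with an episode descriptively, and report the totals beside survival.

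The cost is wording and derivation programming. For ventilation in particular most values will be 0, so mean-based results are fragile and the comparison partly repeats the incidence analysis. Total days also do not correct for early death. With 16 ventilated per arm, 8 vs 4 deaths on ventilator day 3 and survivors at 15 days, the means among the ventilated are (8×15 + 8×3)/16 = 9 and (12×15 + 4×3)/16 = 12. The arm with fewer deaths then shows +3.0 days among the ventilated and 3.0 × 16/104 = +0.46 over all randomised. That is why survival must stand next to the totals.

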4.5 Visit Windows

The following table outlines the analysis visits that data will be mapped to for analysis of efficacy, safety and pharmacodynamics data collected during the study. If after mapping, multiple data points share the same analysis visit, the data point closest to the expected study visit will be used. If there is a tie, the earlier of the visits will be used.

Study Visit	Analysis Visit	Analysis Window
Screening	Screening	-3 to -1
Days 1 – 13	Days 1 – 13	0
Days 14	Days 14	+2 day
Day 28 Follow-up	Day 28	± 2 day
Day 57 Phone Follow-up Visit	Day 57	± 4 day

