a Visit procedures at time of discharge will occur at the date of the dosing visit if visit occurs prior to Day 14, will occur at the Day 14 visit if occurs on Day 14, or will occur on the date of discharge after dosing if after Day 14. This visit is not required if discharge occurs within 2 days after Day 14. If discharge occurs on Day 4, the Day 5 assessments of abbreviated physical exam, safety labs, trough and peak PK, and blood for inflammation markers will not be collected if they were completed as part of the discharge procedures on Day 4.

b Same-day medical record examinations may be used for study purposes to reduce the possible exposure of site staff to COVID-19 risk. Physical examinations may be conducted as standard of care examinations. Abbreviated physical examinations may be conducted by qualified home health care providers or remote/telemedicine visits. Abbreviated physical examinations that cannot be performed at day 5 may be performed up to Day 7.

c WHO Ordinal Scale is derived from subject's oxygen supplementation requirements, hypotension or need for vasopressors, need for renal dialysis, and activity limitations for outpatients.

d Trough PK samples collected within 30 minutes prior to dose.

e ECG and PK sampling to be performed on last day of study treatment if subject remains hospitalized through Day 14. ECG and PK samples are not required on Day 14/EOT if subject is discharged to home before Day 14.

f ECG and PK sampling to be performed at the time of hospital discharge if subject is discharged prior to Day 14. ECG and PK sampling are not required at time of discharge if discharge occurs after the Day 14 visit.

g Peak PK samples collected 3-6 hours after dose.

h Done every other day until 2 qualitative test done at local laboratory is negative. After qualitative test is negative, do viral titer nasopharyngeal testing only on Day 28. For outpatients, scheduled viral titer tests may be skipped on Saturday or Sunday and/or may be skipped if dry ice shipments are not available. In the Saturday or Sunday situation Day 13 tests should be done on the following Monday.

i Safety labs collected within 48 hours prior to consent as part of standard of care can be used to confirm eligibility.

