4.6 Study Days

Study day is defined as the number of days since first dose of IMP and, for a particular date, and is calculated as:

Study day = Assessment date – Date of first dose of IMP + 1, if date of assessment is on or after date of first dose of IMP

or

Study day = Assessment date – Date of first dose of IMP, if date of assessment is prior to the date of first dose of IMP

Therefore, the date of the first dose of IMP will be Day 1.

In the situation where the assessment date is partial or missing, Study Day, and any corresponding durations will appear partial or missing in the listings.

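### The zero-day window for Days 1 to 13 in SAP 4.5 keeps protocol-compliant assessments from Day 4 (discharge), Day 6 and Day 7 out of the descriptive Day 5 by-visit summaries

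*SAP*

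**What the plan says.** **SAP.** Section 4.5 contains a table that "outlines the analysis visits that data will be mapped to for analysis of efficacy, safety and pharmacodynamics data". The row that covers Day 5 reads "Days 1 – 13 Days 1 – 13 0", so the window is zero. The rows for Day 14 (+2), Day 28 (±2) and Day 57 (±4) carry the same windows as protocol Table 1. There is no row for the time-of-discharge visit. The only rule for conflicts is: "If after mapping, multiple data points share the same analysis visit, the data point closest to the expected study visit will be used". Section 4.6 counts study days by calendar date from first dose: "Therefore, the date of the first dose of IMP will be Day 1". Section 1 says that the SAP is based on protocol version 5.0 and takes precedence where the two documents differ.

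**Protocol.** On its first page, Table 1 heads the Day 5 column with a +2 window. Footnote b adds: "Abbreviated physical examinations that cannot be performed at day 5 may be performed up to Day 7". Footnote a deals with subjects who go home on Day 4. It lists the examination, laboratory tests, PK and marker samples otherwise due the next day, and says that these "will not be collected if they were completed as part of the discharge procedures on Day 4".

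**Where Day 5 is used.** SAP 2.3 lists Day 5 among the laboratory time points, and SAP 11.6 lists it for the abbreviated examination. SAP 11.4 summarises laboratory values, changes from baseline and shifts visit by visit. SAP 12 summarises the inflammation markers as observed values and changes, without naming visits.

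**The concern.** The protocol offers a range of days for the Day 5 assessments, but the SAP recognises only one of them. A site that follows the protocol and draws safety laboratory samples on Day 6 or 7 produces a value that the SAP files under a day with no such assessment scheduled. A site that completes the procedures at discharge on Day 4 correctly takes no Day 5 sample, and nothing in the SAP links the Day 4 value to Day 5.

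The Day 5 row of the descriptive tables would then rest on fewer subjects than the protocol intended. Stray Day 4, 6 and 7 rows, each with few subjects, could appear beside it. Because the SAP prevails over the protocol, a programmer cannot simply fall back on Table 1. Two programmers could also produce different Day 5 tables, one using the window table and the other the visit label on the case report form.

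**Working it through.** No sample size, power or alpha figure is involved, so the plan has no figure to reproduce. The check applies the SAP's mapping rule to each day on which the protocol allows a Day 5 assessment.

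**Inputs**
- Permitted days from the Table 1 header: 5 to 5 + 2 = 7, that is Days 5, 6 and 7.
- Permitted day from footnote a: Day 4, if discharge is on Day 4.
- Study day (SAP 4.6): assessment date − first-dose date + 1.
- SAP 4.5 window for Days 1 to 13: 0. An assessment on study day d, with d from 1 to 13, therefore maps to analysis visit d only.

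**Mapping**

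| Collection day | SAP 4.5 as written | Day 5 window of +2 | +2 window and Day 4 substitution |
|---|---|---|---|
| 4 (discharge) | Day 4 | Day 4 | Day 5 |
| 5 | Day 5 | Day 5 | Day 5 |
| 6 | Day 6 | Day 5 | Day 5 |
| 7 | Day 7 | Day 5 | Day 5 |
| Reach Day 5 | 1 of 4 | 3 of 4 | 4 of 4 |

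These are counts of permitted days, not of subjects. The closest-value rule in SAP 4.5 does not help, because it acts only after mapping, on values that already share a visit.

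**Which assessments**
- *Abbreviated examination:* the +2 header, footnote b and footnote a all apply.
- *Safety laboratory tests:* the +2 header and footnote a apply.
- *Inflammation markers:* footnote a names them. Their row is on the continuation page of Table 1, where the header shows Day 5 without +2, so the forward window is not explicit. SAP 1 says that PD reporting is outside the plan, but SAP 4.5 maps PD data and SAP 12 summarises the markers, so I treat them as in scope.
- *Vital signs, oxygen saturation/FiO2 and WHO scale:* scheduled daily through treatment, so a zero window suits them.
- *PK:* SAP 1 and SAP 12 place it outside this plan.

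**Which outputs**
- *Affected:* Day 5 laboratory summaries, category counts and shifts (SAP 11.4); the Day 5 examination summary (SAP 11.6); any Day 5 marker summary (SAP 12).
- *Not affected:* the laboratory shift table for the worst value at any post-baseline visit; the laboratory and examination listings; the Day 28 primary endpoint. SAP 12 mentions no marker listing.

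**The case against.** The strongest reply has three parts.

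1. **Discharge is a scheduled time point in its own right.** Table 1 has a discharge column, and SAP 2.3 and 11.6 name discharge for laboratory tests and examination. After a Day 4 discharge under footnote a, no Day 5 value exists for a window to drop. This stands in part: such values have a planned place, and repeating them at Day 5 is a reporting choice. But the protocol treats the Day 4 procedures as replacing Day 5, and SAP 4.5 has neither a discharge row nor a substitution rule, so the choice has not been made.
2. **Nothing is discarded.** This stands. SAP 4.5 contains no exclusion rule. Day 6 and 7 values move to other analysis visits and remain in the outputs listed as unaffected.
3. **Only descriptive tables are touched.** This also stands. No planned hypothesis test uses a Day 5 laboratory, examination or marker value, and protocol 8.4 intends no formal safety statistics.

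A reader might go further and infer that the missing values all come from subjects sent home early, so that Day 5 would describe the sicker subjects, and that an active drug would lose more values than placebo. The documents do not support this. The +2 header and footnote b are not limited to discharged subjects, although the protocol's change summary ties the laboratory windows to home visits. Home samples taken on Day 5 itself stay at Day 5. No difference in discharge timing between arms is given.

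**Conclusion.** The mismatch is real and lies in the stated rule, not merely in missing detail. SAP 4.5 carries over the protocol windows for Days 14, 28 and 57 but not for Day 5. Following it takes compliant Day 6 and 7 laboratory tests and examinations out of the Day 5 by-visit summaries, and it leaves Day 4 discharge assessments unlinked to Day 5. For the markers, the conclusion is firm for the Day 4 substitution and conditional for Days 6 and 7, until the two Table 1 headers agree.

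The consequence is small: incomplete Day 5 descriptive summaries, with no effect on the primary endpoint or the daily measures. The number of subjects cannot be computed. It is tempting to assume that 30% to 50% are home by Day 5 and that half of their samples fall on Day 4, 6 or 7, which gives 0.30 × 0.5 = 15% to 0.50 × 0.5 = 25%. Neither input is in the documents, so no percentage should be attached to this point.

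**What to change.** In SAP 4.5:

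- Add a Day 5 row with a +2 analysis window, restricted to safety laboratory tests and the abbreviated examination.
- Extend that row to the inflammation markers once the two Table 1 headers have been reconciled.
- Keep the zero window for vital signs, oxygen saturation/FiO2 and the WHO scale.
- State that a Day 4 discharge assessment is used for Day 5 when it replaced the Day 5 assessment under footnote a, and that it is still reported at discharge.

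PK windows belong in the separate PK plan.

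The cost is one assessment-specific row, one sentence and the matching change in the derivation programs. Because the daily measures keep their own window, the row must name the assessments it covers. No new data are needed. If the outputs have already been produced, SAP 1 requires the departure to be documented with its rationale in the study report.
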